1.5 Risks and Benefits for Subjects

Keppra is an antiepileptic drug approved for use in the United States (US) since 1999. Doses of 1000 mg/day to 3000 mg/day are typically used for this indication. As of 2011, Keppra was prescribed to nearly one quarter of all individuals with epilepsy. According to a survey of neurologists, Keppra performs best on categories such as safety/tolerability, as well as subject and physician benefits.

In controlled clinical studies of adults with partial-onset seizures, the most frequently reported adverse events (AEs) from Keppra in combination with other AEDs included somnolence, asthenia, infection, and dizziness. Of the most frequently reported AEs, asthenia, somnolence, and dizziness appeared to occur predominantly during the first 4 weeks of treatment with Keppra. AEs were usually mild-to-moderate in intensity.

Keppra (adult doses 1000 mg/day-3000 mg/day)

Partial onset seizures

Table 3 lists treatment-emergent adverse events (TEAEs) that occurred in at least 1% of adult epilepsy subjects treated with Keppra who participated in placebo-controlled studies and were numerically more common than in individuals treated with placebo.

Confidential Page 31 of 95

Table 3: Incidence (%) of Treatment-Emergent Adverse Events in Placebo-Controlled, Add-On Studies of Adults Experiencing Partial Onset Seizures by Body System

Body System/	Keppra®	Placebo	
Adverse Event	(N=769)	(N=439)	
	%	%	
Body as a Whole			
Asthenia	15	9	
Headache	14	13	
Infection	13	8	
Pain	7	6	
Digestive System			
Anorexia	3	2	
Nervous System			
Somnolence	15	8	
Dizziness	9	4	
Depression	4	2	
Nervousness	4	2	
Ataxia	3	1	
Vertigo	3	1	
Amnesia	2	1	
Anxiety	2	1	
Hostility	2	1	
Paresthesia	2	1	
Emotional Lability	2	0	
Respiratory System			
Pharyngitis	6	4	
Rhinitis	4	3	
Cough Increased	2	1	
Sinusitis	2	1	
Special Senses			
Diplopia	2	1	

Other events reported by at least 1% of adult Keppra-treated subjects, but as or more frequent in the placebo group included: abdominal pain, accidental injury, amblyopia, arthralgia, back pain, bronchitis, chest pain, confusion, constipation, convulsion, diarrhea, drug level increased, dyspepsia, ecchymosis, fever, flu syndrome, fungal infection, gastroenteritis, gingivitis, grand mal convulsion, insomnia, nausea, otitis media, rash, thinking abnormal, tremor, urinary tract infection, vomiting, and weight gain.

Time course of onset of AEs for partial-onset seizures

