Visit type	С	I	I	C major	T ⁶	C minor	T ⁶	C major	C minor	C major	T ⁶	C minor	C major	C major	T/C
[¹⁸ F]MK-6240 (Tau protein marker, optional)				X ¹⁰									X^{10}		
fMRI (JHU only) ¹²			X					X							
Study drug dispensing				X ¹³		X		X	X	X		X			
PK sampling								X		X			X	X	
Biomarker Blood Draw													X	X	
Prior/Concomitant medications ¹⁴	X														
AE/SAE reporting		X													

Abbreviations: AE=adverse event; ApoE=apolipoprotein E; B=baseline; B MRI=baseline magnetic resonance imaging; BPS-O=Behavioral Pattern Separation-Object; C=clinic visit; CBC=complete blood count; CDR=Clinical Dementia Rating; C major=major clinic visit; C minor=minor clinic visit; C-SSRS=Columbia Suicide Severity Rating Scale; D=day; DNA = deoxyribonucleic acid; ECG=electrocardiogram; ET=early termination; FAQ=Functional Activities Questionnaire; FLAIR=fluid attenuation inversion recovery; fMRI = functional magnetic resonance imaging; GDS=Geriatric Depression Scale; HIS=Hachinski Ischemic Scale; I=imaging visit; IR-SPGR=radiofrequency-spoiled gradient echo; ISLT=International Shopping List Test; JHU = Johns Hopkins University; M=month; MMSE=Mini Mental State Examination; MP-RAGE=magnetization-prepared gradient echo; MRI=magnetic resonance imaging; N/A=not applicable; PET=positron emission tomography; PK=pharmacokinetic; S=screening; SAE=serious adverse event; T=telephone contact; T/C=telephone contact/clinic visit; W=week.

The screening phase (S1, S2, S3/B MRI) will occur 7 days to 42 days prior to baseline. Subjects must meet all the criteria during all the screening visits in order to be enrolled in the study. Height without shoes will be recorded in inches or meters.

Baseline visit will occur on day -1 within 12 days ± 2 days of the S3/B MRI visit. S3/B MRI will occur up to 2 weeks prior to Baseline; the Tau scan needs to occur 1 or more days before the cognitive visit.

Week 1 visit will occur 7 days after the baseline visit.

- ⁴ Subjects who discontinue treatment early (ie, at any time after randomization) will have the early termination visit assessments performed as soon as possible after treatment termination.
- All subjects who enroll and subsequently discontinue treatment will be followed up with a phone call during week 78 to assess their medical status and encourage them to come in for a final CDR and neuropsychological assessments and AE reporting.

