- AEs/SAEs and prior medication reporting

3.5.2.2 Randomization and Baseline Visit (Day -1 Within 12 Days ± 2 Days of the S3/B MRI Visit)

The following procedures will be performed and recorded during the baseline visit:

- Randomization of treatment assignment
- Study drug dosing (begins the morning after the baseline visit). Subjects will be given their assigned study drug and instructed to take their 1st dose the next morning
- Vital signs and body weight
- Blood sample for ApoE genotyping (all sites) and DNA banking *(optional procedure;* JHU only)
- A PET scan after injection with the tau PET marker [18F]MK-6240 (optional procedure)
- MMSE, GDS, BPS-O task, trail making test (A and B), FAQ, CDR score (participant and study partner), and C-SSRS assessments
- AEs/SAEs and concomitant medication reporting

3.5.2.3 Weeks 1 (Baseline + 7 Days \pm 2 Days), 17 (Day 119 \pm 5 Days), and 56 (Day 392 \pm 5 Days) Phone Call

A phone call will be made to all the subjects to evaluate at weeks 1, 17, and 56 (for Study Day and time window see Table 7):

- Medical status
- C-SSRS assessment
- AEs/SAEs and concomitant medication reporting

3.5.2.4 Weeks 13, 39, and 65 Visits "Clinic Minor" (Baseline + 13, 39, and 65 Weeks ± 5 Days)

The "clinic minor" visits will take approximately 1 hour each and will include a few basic assessments:

Confidential Page 53 of 95

- Study drug dispensing
- Physical and neurological exams
- Vital signs and body weight
- C-SSRS assessment
- AEs/SAEs and concomitant medication reporting

3.5.2.5 Weeks 26, 52, and 78 "Clinic Major" (Baseline + 26, 52, and 78 Weeks ± 5 Days)

The "clinic major" visits will take approximately 4 hours each and will include a few additional assessments, including neuropsychological testing and blood draws:

- Study drug dispensing (weeks 26 and 52 only)
- Physical and neurological exams
- Vital signs and body weight
- Blood sample for PK testing, serum chemistry, CBC, thyroid panel, and liver function tests
- Urinalysis
- 3T MRI (structural: MP-RAGE or IR-SPGR) at week 26 (JHU only) and at weeks 52 and 78 (all sites)
- 3T fMRI using scanner version of the BPS-O task at Baseline MRI and week 26 only (*optional procedures at JHU only*)
- ISLT, MMSE, BPS-O task, FAQ, CDR score (participant and study partner), and C-SSRS assessments
- AEs/SAEs and concomitant medication reporting

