3.5.3 Early Termination Visit and Early Termination/Follow-up Visit

Subjects who discontinue treatment (ie, at any time after randomization and before the week 78 visit) will have the early termination visit assessments performed as soon as possible after treatment termination. In addition, all subjects who enroll and subsequently discontinue will be followed up with a phone call during week 78 to assess medical status and encourage them to come in to complete the early termination/follow-up visit assessments.

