5.2.7.2 Adverse Events

AEs will be summarized by treatment group and by maximum dose, latest dose received prior to the onset of the AE, by visit and treatment period.

A TEAE is defined as any AE that has an onset on or after the first dose of study drug, or any pre-existing condition that has worsened on or after the first dose of study drug, regardless of the causal relationship to the study drug. TEAEs will be attributed to a treatment using the following rules:

All analyses of AEs will be performed by the study period, so that it is possible to identify AEs that may be related to withdrawal from study treatment. The summaries of AEs will be limited to TEAEs. For summaries of TEAEs, a TEAE will be assigned to a given period if the date of onset of the TEAE is on or after the date of the first visit during the period but before the date of the first visit of the next period.

If the relationship of the AE to study drug is missing, it will be assumed to be related to the study drug for analysis purposes.

The incidence of subjects reporting TEAEs, treatment-emergent SAEs, TEAEs related to study treatment, treatment-emergent SAEs related to study treatment, and TEAEs leading

Confidential Page 73 of 95

to study discontinuation will be summarized using counts and percentages. The total number of TEAEs, treatment-emergent SAEs, TEAEs related to study treatment, treatment-emergent SAEs related to study treatment, and TEAEs leading to study discontinuation will also be summarized.

AEs will be coded using MedDRA. The incidence of TEAEs and treatment-emergent SAEs will be summarized at the subject level by MedDRA primary system organ class and preferred term using counts and percentages.

The incidence of TEAEs and treatment-related TEAEs will also be summarized by maximum severity and by closest relationship to study drug by MedDRA primary system organ class and preferred term. The summary will include the total number and percentage of subjects reporting a particular event. In counting the number of events reported, a continuous event, ie, an event reported more than once and which did not cease, will be counted only once; non-continuous TEAEs reported several times by the same subject will be counted as multiple events.

The incidence of TEAEs resulting in dose reduction will be summarized by the latest dose received and also by treatment group.

Withdrawal-related events will be tabulated separately.

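### Adverse-event periods are bounded by visit dates, so events that start after the last dose but before the early-termination visit are counted as Treatment events

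*Combined protocol and SAP*

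**What the plan says.** Section 5.2.7.2 gives the reason for analysing adverse events by study period: "so that it is possible to identify AEs that may be related to withdrawal from study treatment". It defines a treatment-emergent event (TEAE) by dosing, as "any AE that has an onset on or after the first dose of study drug" (or a worsening from then on). It places the event in a period by visits: the event is "assigned to a given period if the date of onset of the TEAE is on or after the date of the first visit" of that period, "but before the date of the first visit of the next period". No dose date opens or closes a period. The section does not define study period. It promises a separate tabulation of withdrawal-related events, with no definition or time window.

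Two period structures appear elsewhere. Section 3.2 describes a screening period and a 78-week treatment period. Table 7 (Section 3.5.1) has a study-period row with four entries: Screening, Baseline, Treatment and Early termination.

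On the end of treatment, Section 3.5.3 says that subjects who stop early "will have the early termination visit assessments performed as soon as possible after treatment termination", and Table 7 gives that visit no study day. Section 3.4.2 says dosing stops without a taper. Section 5.2.7.1 already uses first and last dosing dates to calculate exposure.

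**The concern.** A by-period table can isolate withdrawal events only if the boundary between Treatment and what follows lies at the end of dosing. Here it lies at a later clinic visit. The days straight after an untapered stop, when a withdrawal event would be most expected, fall on the Treatment side. The Early termination period then holds only events that start on or after a visit whose delay is not limited. A reader of those tables could conclude that few events followed stopping when the rule had placed them elsewhere.

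A similar question arises at the start of dosing, where the answer depends on which period structure is meant.

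**Working it through.** The plan states no figure to reproduce, so the check is to apply the rule to the schedule.

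**Rule (Section 5.2.7.2).** An event belongs to period P if: first visit of P ≤ onset date < first visit of the next period.

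**End of treatment.** Let L be the last dose day and L + g the day of the early-termination visit.

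- Onsets on days L + 1 to L + g − 1 precede the first Early termination visit, so they are labelled Treatment. That is g − 1 full days off drug.
- The documents give no g. For assumed g of 1, 2, 7, 14 and 30 days, the result is 0, 1, 6, 13 and 29 days.
- Illustration with assumed dates: last dose day 200, visit day 214. Onsets on days 201 to 213 are labelled Treatment; day 214 is the first day labelled Early termination.
- If the visit is missed and the subject is next seen at the week-78 follow-up (day 546), the same subject has 546 − 200 − 1 = 345 off-drug days labelled Treatment.
- Under Section 3.2, the treatment period has no successor, so every off-drug onset is a Treatment event whatever g is.

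For scale, Section 1.3 gives a half-life of 7.56 to 8.09 h. Taking five half-lives as washout (a convention, assumed here): 5 × 7.56 = 37.8 h and 5 × 8.09 = 40.5 h. Adding the 2.5 h longer half-life that Section 1.5 reports for elderly subjects gives 5 × 10.06 = 50.3 h and 5 × 10.59 = 53.0 h. A visit more than about two days after the last dose therefore puts the whole washout under Treatment.

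**Start of treatment, Table 7 reading only.**

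- The baseline visit is on day −1, and the first dose is the next morning (Section 3.5.2.2), taken as day 1.
- The Table 7 footnote reads "Week 1 visit will occur 7 days after the baseline visit", and the table gives day 7 ± 2. Section 3.2 counts telephone contacts as visits, so this call is the first Treatment visit.
- On-drug days labelled Baseline = Week 1 day − 1: 5 − 1 = 4, 7 − 1 = 6, 9 − 1 = 8.
- As a share of 546 days: 4/546 = 0.7%, 6/546 = 1.1%, 8/546 = 1.5%. As a share of the first 28 days: 4/28 = 14%, 6/28 = 21%, 8/28 = 29%.
- The 28-day comparison is relevant because Section 1.5 says that asthenia, somnolence and dizziness "appeared to occur predominantly during the first 4 weeks of treatment with Keppra". That observation is at 1000 to 3000 mg/day, not at 220 mg.

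**Start of treatment, Section 3.2 reading.** If the baseline visit opens the treatment period, onsets from day 1 are Treatment events and no on-drug day is misplaced.

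**The case against.** The strongest case against has five parts.

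1. *The Baseline problem comes from one reading.* Section 3.2 names only screening and treatment. Section 4.2.1 identifies the start of treatment with the first dose. Drug is dispensed at the baseline visit, and a Baseline category makes little sense for events that by definition begin on or after the first dose. This stands. A reader might infer that the plan files first-week events as Baseline; the documents support that only if the Table 7 columns are the periods. What remains is that the term is undefined and a programmer could use Table 7.

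2. *Completers.* A reader might infer that every post-dose event in completers is misfiled. The label would indeed be Treatment, but week 78 is a completer's last scheduled visit. After it, Section 4.2.1 asks only for events detected within 1 month and considered possibly related or related, and Section 4.2.2 for related serious events. Very few recorded events are involved.

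3. *The effect cannot be sized.* A reader might want to state a share of withdrawal events lost. If onset were exponential with mean 4 days, 1 − exp(−g/4) would give 53%, 83% and 97% for delays of 3, 7 and 14 days. Both the mean and the delays are invented, and the visit is meant to be prompt. These are not findings about this trial.

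4. *Other outputs help.* Overall TEAE and serious-event incidence uses a dose-based definition and the same rule in both arms, so it is unaffected. The listing gives onset relative to first dose; combined with exposure days, off-drug onsets can be recovered by hand. The separate withdrawal tabulation could also help. All true, but that tabulation has no criterion, and recovery by hand is not an analysis.

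5. *A detailed SAP is to follow (Section 5.2).* It could define the periods. Section 5.2.7.2 nevertheless states a specific rule and does not defer this point.

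None of these removes the end-of-treatment problem, which arises under both period structures.

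**Conclusion.** The rule as written works against its own stated purpose. Whenever at least one full day separates the last dose from the early-termination visit, onsets in that gap are labelled Treatment. The gap has no upper limit in the documents, and under Section 3.2 there is no post-treatment period to receive these events. This follows from the text and needs no assumption about event timing.

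The mislabelling of 4 to 8 early on-drug days as Baseline is conditional on the Table 7 reading. The number of misplaced events is unknown, since neither the visit delay nor the timing of withdrawal events is given. A subject who stops on the day of the visit, or the day before, contributes no full misplaced day.

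The damage is confined to the by-period and withdrawal tabulations. It does not reach the TEAE definition or the overall comparison of incidence between arms. It should be corrected before the analysis plan is signed, but it does not put the main safety summary in doubt.

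**What to change.** In Section 5.2.7.2, define the periods and replace visit dates with dose dates:

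- On-treatment: onset from the first dose date to the last dose date, plus any short washout window that the sponsor specifies in advance.
- Off-treatment: onset after that.
- Draw the withdrawal-related tabulation from the off-treatment phase, with denominators limited to subjects who have follow-up in it. Otherwise completers with almost no off-drug observation would dilute the percentages.

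Do not use the imputed last-dose dates of Section 5.2.7.1 for this flag. That section sets a missing last-dose date to the last dispensing date and a month-only date to the first of the month. Table 7 dispenses every 13 weeks, so the first rule could move up to about 13 × 7 = 91 genuinely on-drug days into the off-treatment phase. Where the last-dose date is missing or partial, treat the event as on-treatment unless the available dates show that it began after the last dose, and report how many such cases there are.

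The cost is one extra derivation and a partial-date rule. First and last dosing dates are already needed for the exposure calculation. The change concerns classification in the analysis only; dosing and clinical management are untouched.

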3 INVESTIGATIONAL PLAN

3.1 Overall Study Design and Plan

[figure not shown]
This is a multicenter, randomized, double-blind, placebo-controlled, 78-week, fixed-dose study evaluating AGB101 versus placebo as a treatment for slowing the progression of MCI due to AD.

The screening phase will occur 7 days to 42 days before the baseline visit (see Figure 4). After providing informed consent, subjects who meet entry criteria will be randomized 1:1 during the final baseline visit to receive either placebo or AGB101. A total of 160 subjects will be randomized (80/treatment group). Because of the PK and safety profile of AGB101, dosing will be initiated without titration and will be discontinued without tapering.

The baseline visit will occur 1 day before the study start. Subjects will be given their assigned study drug and instructed to take their 1st dose the next morning. A telephone contact will be made 1 week after the baseline visit to assess the subjects' medical status and inquire about any AEs/SAEs; similar telephone contacts will be made at weeks 17 and 56 with the same purpose. Study clinic visits are divided into minor visits ("clinic minor") at weeks 13, 39, and 65 and major visits ("clinic major") at weeks 26, 52, and 78. The difference between these two types of visits is the number and kinds of assessments performed. The "clinic minor" visits consist of a few basic assessments, while the "clinic major" visits consist of more in-depth testing, neuropsychological testing, and blood draws.

Subjects who enroll and subsequently discontinue the treatment before the 78-week visit will be followed up with a phone call at week 78 to assess their medical status and encourage them to come in to complete the early treatment termination/follow-up visit assessments.

Figure 4: Study Schema

Confidential Page 39 of 95

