3.4.2 Dosage Schedule

Subjects will be administered a single morning daily dose of placebo or AGB101 for 78 weeks. Given the low dose being used, AGB101 dosing will be initiated without titration and will be discontinued without tapering.

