3.4.6 Treatment Compliance

Study drug containers must be returned at each visit, as compliance will be assessed by tablet count. Noncompliance is defined as taking < 80% or > 120% of the study drug during any outpatient evaluation period (visit to visit). The investigator may use clinical judgement in evaluating noncompliance with the study drug as a reason for early termination from the study. Subjects who discontinue treatment will not be automatically discontinued from the study. Every effort should be made to bring subjects back for study visits unless the subject withdraws consent.

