Narratives of deaths, SAEs, and other significant AEs will be provided in the relevant section of the study report.

A complete subject listing of all AEs will be provided in the study report. This listing will include treatment, AE verbatim term, MedDRA primary system organ class and preferred term, the time of onset and cessation of the event relative to the first dose of study drug, duration of the AE, whether serious or not, severity, relationship to study drug, action taken, and outcome.

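### Section 5.2.7.2 plans no summary of TEAEs that led to stopping study drug, although subjects who stop drug are kept in the study

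*Combined protocol and SAP*

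**What the plan says.** Section 5.2.7.2 (Adverse Events) gives incidence and event counts for several classes of TEAE. The only class defined by stopping is study discontinuation: for incidence, "to study discontinuation will be summarized using counts and percentages"; for event totals, "and TEAEs leading to study discontinuation will also be summarized". A second summary concerns dose: "The incidence of TEAEs resulting in dose reduction will be summarized by the latest dose received and also by treatment group". The same section also splits AEs by maximum dose and by latest dose before onset.

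On dosing, Section 3.1 describes the design: "This is a multicenter, randomized, double-blind, placebo-controlled, 78-week, fixed-dose study evaluating AGB101 versus placebo". Section 3.4.2 adds: "Subjects will be administered a single morning daily dose of placebo or AGB101 for 78 weeks". Table 6 lists a single strength, one 220 mg tablet, and there is no titration or taper.

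On stopping, Section 3.4.6 says: "Subjects who discontinue treatment will not be automatically discontinued from the study". Sections 3.3.3 and 5.2.2 repeat this. Sections 3.1 and 3.5.3 provide a week 78 telephone call to subjects who stopped treatment, to encourage a follow-up visit.

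Two other outputs bear on the point. Section 5.2.3 summarises the reason for early discontinuation by treatment group. The full AE listing in Section 5.2.7.2 includes "severity, relationship to study drug, action taken, and outcome".

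**The concern.** Tolerability is part of the safety objective (Section 2.5). With one dose and no reduction step, stopping the drug is the main way in which poor tolerability shows in treatment received. The AE section counts a different event, leaving the study, and adds a dose change for which the protocol has no provision.

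The two kinds of stopping are deliberately kept apart in this protocol, because the intention-to-treat analysis wants week 78 data from subjects who are off drug. That is sound for efficacy. For the AE summary as worded, it means that every such subject retained is one fewer counted. Better follow-up would make AGB101 look better tolerated in that table, with no change in how many subjects stopped taking it because of an AE.

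**Working it through.** The plan states no figure on this point, so the check is to follow each possible path through the planned outputs, using Sections 3.3.3, 3.4.2, 3.4.6, 5.2.3 and 5.2.7.2 read literally.

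| Path | TEAEs leading to study discontinuation | TEAEs resulting in dose reduction | Disposition (5.2.3) | AE listing |
|---|---|---|---|---|
| TEAE, stops drug, leaves study | counted | no | yes, if AE is the primary reason | yes |
| TEAE, stops drug, stays to week 78, AE is the primary reason | not counted | no | yes, if the table covers stopping treatment | yes |
| TEAE contributes, stops drug, stays to week 78, another reason is primary | not counted | no | shown under the other reason | yes |
| TEAE, dose reduced under the protocol | not applicable | no such step exists | not applicable | not applicable |

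The second and third rows are the gap. The fourth shows why the dose-reduction summary cannot fill it. A subject who simply took fewer tablets would be handled as noncompliant (below 80%, Sections 3.4.6 and 5.2.2), not as dose-reduced.

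The direction follows from simple algebra. Let S be the number in an arm who stop drug because of a TEAE, and r the fraction of them who remain in the study.

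- Number shown in the literal summary = S × (1 − r).
- Share of AE-driven stopping that is shown = S(1 − r) / S = 1 − r.
- With r = 0 the summary is complete; with r = 0.5 it shows half; as r approaches 1 it approaches zero.
- With the same r in both arms, the difference shown is (1 − r) times the true difference. If r differs by arm, the comparison is also distorted.

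The documents give neither S nor r for this trial.

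The dose-level wording is not confined to one sentence. Section 5.2.7.1 asks for days of exposure to each dose, and Section 5.2.7.3 contrasts active dose as well as active drug with placebo. With one dose, these splits are empty or repeat the arms.

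**The case against.** The strongest reply is that little is lost. Section 3.3.3 is headed as early termination from treatment, requires a termination form for every subject who received drug, and has an adverse-event category covering serious and non-serious events regardless of relatedness. Section 5.2.3 then reports the reason by arm. All TEAEs are tabulated by system organ class and preferred term, and each is listed with action taken. This stands, and it rules out a stronger reading that a reader might infer: that tolerability failures go unrecorded. They do not. But disposition carries one primary reason per subject and no event term, and a listing is not a comparison by arm.

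A second reply is that the protocol uses its terms loosely. Sections 3.4.6 and 5.2.2 treat drug noncompliance as a possible reason for early termination from the study, and several categories in Section 3.3.3 speak of the study under a heading about treatment. A programmer might therefore count drug stoppers under study discontinuation. That is possible, but it means that two programmers could produce different counts, which is itself a reason to fix the wording.

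Third, Section 5.2.7.2 promises a separate table of withdrawal-related events. The term is undefined. Beside that section's stated purpose of identifying AEs related to withdrawal from treatment, it more likely means events after stopping than events that caused it.

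Fourth, Section 5.2 defers detail to a SAP to be finalised before database lock, and that SAP may already contain the table. This stands, and it also makes the SAP a natural place for the fix.

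**Conclusion.** The point holds as a specific gap. Section 5.2.7.2 ties its discontinuation summary to leaving the study, in a protocol that keeps drug stoppers in the study, and pairs it with a dose-reduction summary that a one-strength trial cannot populate. The missing output is the by-arm count, with event terms, of TEAEs that led to stopping drug, including those where the AE was not the primary reason.

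No reliable size can be given. A reader might multiply the levetiracetam rates in Section 1.5 by 80 per arm: 80 × 3.7% = 3.0 up to 80 × 17.2% = 13.8 subjects, or 80 × 14% = 11.2 against 80 × 7% = 5.6. The documents do not support this. The 14% and 7% pool dose reductions with study discontinuation, the 3.7% is described as leaving the study, and the 17.2% comes from epilepsy patients at a median of 950 mg a day, against 220 mg here. A reader might also infer that the planned table would show zero in both arms. That needs every AE-driven stopper to remain in the study. Yet Section 3.4.4 withdraws subjects unblinded by the investigator, and the physician-decision category in Section 3.3.3 covers removal from the study for safety risk.

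The conclusion assumes a literal reading of study discontinuation and that the SAP does not already add the summary. The empty dose splits, taken alone, are a matter of tidying.

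**What to change.** In Section 5.2.7.2, or in the SAP still to be finalised:

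1. Add the incidence and number of TEAEs leading to permanent discontinuation of study drug, by arm and by system organ class and preferred term. Take them from the AE action-taken field, after confirming that its response categories include drug withdrawn; Section 4 names the field but not its categories.
2. Keep TEAEs leading to study discontinuation as a separate row.
3. State in Section 5.2.3 whether early discontinuation means treatment or study, and define withdrawal-related events.
4. Reconcile the dose-reduction, maximum-dose and latest-dose summaries with the fixed-dose design in Sections 3.1 and 3.4.2. On the current text they are empty or repeat the arms, and can be removed.

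The cost is SAP and table-shell wording. Action taken is already recorded for each AE, so no new data collection is needed provided that its categories are adequate. Clinical management does not change.
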